7.6 Withdrawal of consent for sample collection and/or retention

A patient may withdraw consent to provide samples for research at any time without giving a reason. The Investigator must ensure that their wishes are recorded in the medical record and will inform the Trial Office accordingly. The Investigator should discuss with patients the valuable use of samples that have already been provided and under circumstances where these samples have already been processed and anonymised, it would not be possible to destroy such samples.

8 INVESTIGATIONAL MEDICINAL PRODUCTS (IMP)

The trial is investigating the unlicensed drug M6620 (Berzosertib) in combination with the radiotherapy (stage A1); M6620 (Berzosertib) in combination with chemotherapy agents Cisplatin and Capecitabine (stage A2) and M6620 (Berzosertib) with chemoradiotherapy (stage B). For the purposes of the trial, M6620 (Berzosertib), Cisplatin and Capecitabine are all considered IMPs.

8.1 Stage A1 Treatment

Two M6620 (Berzosertib) dose levels and 3 dosing frequencies (treatment schedules) are proposed. Both the dose and frequency of M6620 (Berzosertib) will vary but the administered radiation dose and fractionation schedule will remain unchanged across treatment plans. The treatment schedule will last for 3 weeks and radiotherapy must start on a Monday.

Antiemetics should be prescribed as supporting medication to be available from Day 1 of Radiotherapy, (i.e. Domperidone 20mg tds prn PO 5/7 or Metoclopramide 20mg tds prn PO 5/7, or the preferred standard of care at the institution)

8.1.1 M6620 (Berzosertib) treatment schedules - Stage A1

The starting dose of M6620 (Berzosertib) will be 140mg/m² IV once weekly (schedule 1). If schedule 1 is too toxic, the trial will be re-started at 90mg/m² (schedule -3). For all schedules see table 8.1. The treatment schedule of M6620 (Berzosertib) will be escalated or de-escalated using the TiTE-CRM model (see section 2 for further details).

Table 8.1

Dose Escalation schedule	
Treatment schedule	Dose** of M6620 (Berzosertib) and days of the schedule it will be delivered
-3	90 mg/m ² day 2, 9, 16
-2	90 mg/m ² day 2, 5, 9, 12, 16
-1	90 mg/m ² day 2, 5, 9, 12, 16, 19
1*	140 mg/m ² day 2, 9, 16
2	140 mg/m ² day 2, 5, 9, 12, 16
3	140 mg/m ² day 2, 5, 9, 12, 16, 19
4	240 mg/m ² day 2, 9, 16
5	240 mg/m ² day 2, 5, 9, 12, 16
6	240 mg/m ² day 2, 5, 9, 12, 16, 19

*Starting dose and schedule. 90mg/m² dose will only be explored if trial is re-started

**Doses are stated as exact dose in units. No intermediate dose levels or further splitting of the dose allowed

8.1.2 Radiotherapy dose and duration –Stage A1

The total dose of radiation will be 35Gy in 15 fractions treated once daily, 5 days a week Monday to Friday and prescribed and recorded per ICRU 62.

8.1.3 Stage A1: Dose Escalation Schema

Schedule -3 – 90 mg/m², 270 mg/m² per plan

	Week 1							Week 2							Week 3						
	M	T	W	T	F	S	S	M	T	W	T	F	S	S	M	T	W	T	F	S	S
Radiotherapy	X	X	X	X	X			X	X	X	X	X			X	X	X	X	X		
ATR Inhibitor		M						M							M			M			

Schedule -2 – 90 mg/m², 450 mg/m² per plan

	Week 1							Week 2							Week 3						
	M	T	W	T	F	S	S	M	T	W	T	F	S	S	M	T	W	T	F	S	S
Radiotherapy	X	X	X	X	X			X	X	X	X	X			X	X	X	X	X		
ATR Inhibitor		M		M				M			M				M		M		M		

Schedule -1 – 90 mg/m², 540 mg/m² per plan

	Week 1							Week 2							Week 3						
	M	T	W	T	F	S	S	M	T	W	T	F	S	S	M	T	W	T	F	S	S
Radiotherapy	X	X	X	X	X			X	X	X	X	X			X	X	X	X	X		
ATR Inhibitor		M		M				M			M				M		M		M		

Schedule 1 – 140 mg/m² per dose, 420 mg/m² per plan (starting schedule)

	Week 1							Week 2							Week 3						
	M	T	W	T	F	S	S	M	T	W	T	F	S	S	M	T	W	T	F	S	S
Radiotherapy	X	X	X	X	X			X	X	X	X	X			X	X	X	X	X		
ATR Inhibitor		M						M			M				M		M		M		

Schedule 2 – 140 mg/m², 700 mg/m² per plan

	Week 1							Week 2							Week 3						
	M	T	W	T	F	S	S	M	T	W	T	F	S	S	M	T	W	T	F	S	S
Radiotherapy	X	X	X	X	X			X	X	X	X	X			X	X	X	X	X		
ATR Inhibitor		M		M				M			M				M		M		M		

Schedule 3 – 140 mg/m², 840 mg/m² per plan

	Week 1							Week 2							Week 3						
	M	T	W	T	F	S	S	M	T	W	T	F	S	S	M	T	W	T	F	S	S
Radiotherapy	X	X	X	X	X			X	X	X	X	X			X	X	X	X	X		
ATR Inhibitor		M		M				M			M				M		M		M		

Schedule 4 – 240 mg/m², 720 mg/m² per plan

	Week 1							Week 2							Week 3						
	M	T	W	T	F	S	S	M	T	W	T	F	S	S	M	T	W	T	F	S	S
Radiotherapy	X	X	X	X	X			X	X	X	X	X			X	X	X	X	X		
ATR Inhibitor		M			M			M			M				M		M		M		

Schedule 5 – 240 mg/m², 1200 mg/m² per plan

	Week 1							Week 2							Week 3						
	M	T	W	T	F	S	S	M	T	W	T	F	S	S	M	T	W	T	F	S	S
Radiotherapy	X	X	X	X	X			X	X	X	X	X			X	X	X	X	X		
ATR Inhibitor		M			M			M			M				M		M		M		

Schedule 6 – 240 mg/m², 1440 mg/m² per plan

	Week 1							Week 2							Week 3						
	M	T	W	T	F	S	S	M	T	W	T	F	S	S	M	T	W	T	F	S	S
Radiotherapy	X	X	X	X	X			X	X	X	X	X			X	X	X	X	X		
ATR Inhibitor		M			M			M			M				M		M		M		

8.2 Stage A2 Treatment

Two dose levels and 2 dosing frequencies (treatment schedules) are proposed. Both the dose and frequency of M6620 (Berzosertib) will vary but the Cisplatin and Capecitabine dose and schedule will remain unchanged across treatment plans. The treatment schedule will last for 6 cycles (18 weeks).

8.2.1 M6620 (Berzosertib) treatment schedule – Stage A2

The starting dose of M6620 (Berzosertib) will be 90mg/m² IV once weekly (schedule 1). For all schedules see table 8.2. The treatment schedule of M6620 (Berzosertib) will be escalated or de-escalated using the TiTE-CRM model (see section 2 for further details).

Table 8.2

Dose Escalation schedule	
Treatment schedule	Dose of M6620 (Berzosertib) and days of the schedule it will be delivered
1	90 mg/m ² once a week for 18 weeks (Tuesdays)
2	90 mg/m ² twice a week for 18 weeks (Tuesdays and Fridays)
3	140 mg/m ² once a week for 18 weeks (Tuesdays)
4	140 mg/m ² twice a week for 18 weeks (Tuesdays and Fridays)

*Doses are stated as exact dose in units. No intermediate dose levels or further splitting of the dose allowed

8.2.2 Chemotherapy dose and duration - Stage A2

Chemotherapy (Weeks 1 – 18)

Cisplatin 60mg/m² IV Day 1 of 21-day cycle for 6 cycles
 Capecitabine 625mg/m² po bd Days 1-21 of 21-day cycle for 6 cycles

8.2.3 Stage A2 Dose escalation schema

Dosing schedule 1,3		Week 1						Week 2						Week 3									
		M	T	W	T	F	S	S	M	T	W	T	F	S	S	M	T	W	T	F	S	S	
	Capecitabine	→	→	→	→	→	→		→	→	→	→	→	→	→	→	→	→	→	→	→	→	
	Cisplatin	C																					
	ATR Inhibitor			M							M								M				

Repeat this 3 weekly schedule for 6 cycles

Dosing schedule 2,4		Week 1						Week 2						Week 3									
		M	T	W	T	F	S	S	M	T	W	T	F	S	S	M	T	W	T	F	S	S	
	Capecitabine	→	→	→	→	→	→		→	→	→	→	→	→	→	→	→	→	→	→	→	→	
	Cisplatin	C																					
	ATR Inhibitor			M							M								M			M	

Repeat this 3 weekly schedule for 6 cycles

8.3 Stage B Treatment

The dose administered in stage B will be 140mg/m² (see section 2.3) and will remain constant whilst three dosing schedules are explored (see table 8.3). The chemotherapy and radiation doses and fractionation schedules will remain unchanged across dosing schedules.

The 11 weeks of treatment consists of 6 weeks of induction chemotherapy (Capecitabine and Cisplatin) with M6620 (Berzosertib) followed by 5 weeks of concomitant chemoradiotherapy (Capecitabine, Cisplatin and radiotherapy) with M6620 (Berzosertib). All patients will receive M6620 (Berzosertib) with induction chemotherapy on Cycle 1 Day 2 and Cycle 2 Day 2. In the last week of chemotherapy patients will be assigned to a M6620 (Berzosertib) treatment schedule to be administered during chemoradiotherapy (see table 8.3 below). Radiotherapy must start on a Monday.

8.3.1 M6620 (Berzosertib) Treatment dose and schedule – Stage B

The dose of M6620 (Berzosertib) in Stage B will be 140mg/m², allocation will start on schedule 1.

Table 8.3

Dose Escalation Schedule		
Treatment Schedule	M6620 (Berzosertib) administration during induction chemotherapy	M6620 (Berzosertib) administration during Chemoradiotherapy
-1	Cycle 1 day 2, Cycle 2 day 2	Days 2, 9, 16, 23, 30
1*	As above	Days 2, 5 , 9, 16, 23, 26 , 30
2	As above	Days 2, 5, 9, 12, 16, 19 , 23, 26, 30, 33

*Starting schedule. Reduced frequency schedule (-1) will only be explored if schedule 1 is too toxic.

8.3.2 Chemoradiotherapy dose and duration - Stage B

Induction Chemotherapy (Weeks 1 – 6)

Cisplatin 60mg/m² IV Day 1 of 21-day cycle for 2 cycles (Days 1 and day 22 of chemotherapy)
Capecitabine 625mg/m² po bd Days 1-21 of 21-day cycle for 2 cycles

Concurrent chemoradiotherapy (Weeks 7 – 11)

Cisplatin 60mg/m² IV Day 1 of 21-day cycle for 2 cycles (Days 1 and day 22 of chemoRadiotherapy)
Capecitabine 625mg/m² po bd on days receiving radiotherapy (From day 1 to day 33 of chemoradiotherapy **excluding** days not receiving radiotherapy) (Total 25 days of treatment)

8.3.3 Radiotherapy dose and duration - Stage B

The total dose of radiation will be 50Gy in 25 fractions treating once daily, 5 days per week Monday to Friday and prescribed and recorded as per ICRU 62.

8.3.4 Stage B Dose frequency escalation schema

Induction Chemotherapy - All patients

	Week 1							Week 2							Week 3						
	M	T	W	T	F	S	S	M	T	W	T	F	S	S	M	T	W	T	F	S	S
Capecitabine	→	→	→	→	→	→	→	→	→	→	→	→	→	→	→	→	→	→	→	→	→
Cisplatin	C																				
ATR Inhibitor		M																			

	Week 4							Week 5							Week 6						
	M	T	W	T	F	S	S	M	T	W	T	F	S	S	M	T	W	T	F	S	S
Capecitabine	→	→	→	→	→	→	→	→	→	→	→	→	→	→	→	→	→	→	→	→	→
Cisplatin	C																				
ATR Inhibitor		M																			

Chemoradiotherapy dosing frequency escalation schema

Dosing schedule -1		Week 7					Week 8					Week 9					Week 10					Week 11							
		M	T	W	T	F	S	S	M	T	W	T	F	S	S	M	T	W	T	F	S	S	M	T	W	T	F	S	S
	Capecitabine																												
	Cisplatin	C																											
	Radiotherapy	X	X	X	X	X			X	X	X	X	X			X	X	X	X	X			X	X	X	X	X		
	ATR Inhibitor			M						M							M								M				

Dosing schedule 1		Week 7					Week 8					Week 9					Week 10					Week 11							
		M	T	W	T	F	S	S	M	T	W	T	F	S	S	M	T	W	T	F	S	S	M	T	W	T	F	S	S
	Capecitabine																												
	Cisplatin	C																											
	Radiotherapy	X	X	X	X	X			X	X	X	X	X			X	X	X	X	X			X	X	X	X	X		
	ATR Inhibitor			M			M			M							M							M			M		

Dosing schedule 2		Week 7					Week 8					Week 9					Week 10					Week 11							
		M	T	W	T	F	S	S	M	T	W	T	F	S	S	M	T	W	T	F	S	S	M	T	W	T	F	S	S
	Capecitabine																												
	Cisplatin	C																											
	Radiotherapy	X	X	X	X	X			X	X	X	X	X			X	X	X	X	X			X	X	X	X	X		
	ATR Inhibitor			M			M			M			M				M			M				M			M		

8.4 Management of M6620 (Berzosertib) drug administration

M6620 (Berzosertib) will be administered intravenously over 60 minutes (\pm 10 minutes) approximately one hour after radiotherapy in stage A1 and B. When the total volume of infusion exceeds 600mL, the infusion may be extended by up to 30 minutes. Intravenous administration of M6620 (Berzosertib) is independent of food intake. When given after chemotherapy, the M6620 (Berzosertib) should be initiated approximately 24 hours (+/- 4hours) after cessation of cisplatin infusion (continue with Capecitabine as prescribed). The cannula should be removed following each infusion. Consideration of a Peripheral Inserted Catheter should be given if there are difficulties accessing a vein.

M6620 (Berzosertib) is associated with infusion-related reactions, e.g., infusion site erythema, infusion site reaction, and catheter site related reaction. Infusion reactions are common with IV administration of drugs used to treat cancer. These reactions occur during or shortly after administration of the drug and are diverse. They may include pruritus, flushing, chills/rigors, urticaria/rash, headache, bronchospasm/dyspnea, and hypotension or hypertension, among others. Infusion-related reactions, nausea, and vomiting are considered adverse drug reactions (ADRs) for MK6620.

The infusion can be mildly irritating so it is necessary to monitor the intravenous catheter site closely for evidence of erythema, tenderness or induration. To minimize the possibility of phlebitis, M6620 (Berzosertib) should be administered through a large bore catheter into a large caliber peripheral vein. The intravenous infusion site should be monitored closely for the development of erythema, induration, purulence, tenderness, or warmth. If any subject develops phlebitis, or signs or symptoms of inflammation that may progress to phlebitis or that the patient cannot tolerate, standard measures should be employed to ameliorate these symptoms (including removal of the infusion catheter and resumption of infusion through a different vein).

If any subject develops pruritus, flushing, or any other symptom suggestive of a systemic infusion reaction, standard measures should be employed to manage these symptoms (e.g. antihistamines and/or steroids, fluid support). Any non-serious reaction such as pruritis, can be prevented in subsequent administration by appropriate desensitizing measures prior to the administration of the study drugs as long as they are not prohibited by protocol (e.g. Corticosteroid and antihistamine combinations that may be used include: 100 mg to 200 mg hydrocortisone intravenously approximately 60 minutes (\pm 15 minutes) before M6620 (Berzosertib) infusion, and either 10 mg of chlorphenamine intravenously approximately 30 minutes (\pm 10 minutes) before M6620 (Berzosertib) infusion. Alternative antihistamine and steroid doses, timing, routes of administration and agents may be considered, as long as not prohibited by protocol. In addition, treatment with an H2-blocker (e.g., ranitidine) may be considered for subjects not responsive to a regimen with an H1-blocker. If standard procedures to limit symptoms of an infusion reaction have failed, further re-challenges are prohibited.

Serious acute hypersensitivity reactions have occurred in a few subjects receiving M6620 (Berzosertib). These reactions occurred within minutes of re-exposure to M6620 (Berzosertib), and in cases reported to date, they have occurred during the second infusion. They may include hypotension and mental status changes. All subjects have fully recovered with standard treatment for this reaction, including immediate discontinuation of the inciting infusion and administration of IV corticosteroid and antihistamine, as well as IV fluids and oxygen when clinically indicated. If a serious acute hypersensitivity reaction occurs M6620 (Berzosertib) should be permanently withdrawn and reported as an SAR. For management of M6620 (Berzosertib) toxicity or missed doses see section 9.3.

Laboratory values required for administration of M6620 (Berzosertib) and chemotherapy

Laboratory parameter	Cycle 1 Day 1	Day 1 of subsequent cycles	Other days M6620 (Berzosertib) administered alone or with Capecitabine
Haemoglobin	$\geq 8.0\text{g/dL}$ Stage A1; $\geq 10.0\text{g/dL}$ Stage A2/B	$\geq 8.0\text{g/dL}$ Stage A1/A2; $\geq 10.0\text{g/dL}$ Stage B(during radiotherapy)	$\geq 7.0\text{g/dL}$ (if asymptomatic)
Absolute neutrophil count	$\geq 1.5 \times 10^9/\text{L}$	$\geq 1 \times 10^9/\text{L}$	$\geq 1.0 \times 10^9/\text{L}$
Platelet count	$\geq 100 \times 10^9/\text{L}$	$\geq 75 \times 10^9/\text{L}$	$\geq 75 \times 10^9/\text{L}$

AST/ALT	≤2.5 X ULN or ≤5 X ULN if liver metastases	≤2.5 X ULN or ≤5 X ULN if liver metastases	≤2.5 X ULN or ≤5 X ULN if liver metastases or capecitabine given alone
Estimated glomerular filtration rate	≥40mL/min A1 or ≥60mL*/min Stage A2/B	≥60mL/min Stage A2/B	Not required
Total Bilirubin (serum)	≤1.5 X ULN ^a	Not required	Not required

a – unless subject has known or suspected Gilbert's syndrome

* if below 60ml/min, formal Creatinine clearance required (EDTA glomerular function rate, or 24 hours urine collection), and 100% dose cisplatin may be administered if formal result is ≥50ml/min

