8.6 Management of cisplatin administration

Cisplatin will be administered on day 1 of a 3 weekly cycle. From weeks 1 to 18 for Stage A2 and 1-11 for Stage B as an intravenous infusion at 60mg/m² over 2 hours on treatment days or as per local policy. The hydration regimen for cisplatin administration will be determined by locally agreed pharmacy procedures and guidelines. Pre and post anti-emetics should be given according to local practice for high risk emesis. Laboratory values required for administration of chemotherapy will be as per standard policy (for administration of M6620 (Berzosertib) see section 8.4). Patient monitoring and management of hypersensitivity and extravasation will be as per local hospital policy. Patients with significant hearing impairment will be made aware of potential ototoxicity. For those who choose to be included, it is recommended that audiograms be carried out at baseline and prior to cycle 2. Gastric protection (Proton Pump inhibitor or H2 blocker) is recommended for all patients for duration of therapy and for at least 6 weeks thereafter.

On days of concurrent chemo-radiation, cisplatin should be completed before radiotherapy treatment. Patients may undergo their radiotherapy during the post-hydration following cisplatin, which may be interrupted provided it is completed afterwards.

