8.8 Laboratory values required for administration of chemotherapy

See table in section 8.4.

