9.4 Management of chemotherapy toxicities

Toxicity due to capecitabine or cisplatin administration may be managed by symptomatic treatment and/or modification of the dose (treatment interruption or dose reduction) as per standard of care. Once the dose has been reduced, it should not be increased at a later time. Patients taking capecitabine should be informed of the need to interrupt treatment immediately if moderate or worse toxicity occurs. Detailed information can be found in the product SPCs available from www.medicines.org.uk.

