9.4.4 Additional Cisplatin toxicities

Nephrotoxicity

Cisplatin produces cumulative nephrotoxicity. If a baseline estimate of renal function using the Cockroft & Gault formula predicts the GFR to be ≥ 60mL/min full dose cisplatin should be used. If the estimate is <60mls/min a formal measure of Creatinine clearance should be performed (EDTA or 24 hour urine test) and the appropriate cisplatin dose used (see table below). In the case of a 25% deterioration in estimated renal function (using the Cockroft & Gault formula) on pre-

treatment blood samples a formal Creatinine clearance test should be performed and pending this an appropriate dose reduction in cisplatin should be made. The formal Creatinine clearance result, when available, takes precedent over estimated GFR for subsequent cisplatin dose calculations.

GFR (mls/min) Baseline and prior to Day 1	Cisplatin Dose
≥ 60ml/min	100%
45-59ml/min	50%
30-44 ml/min	Stop Cisplatin. This group of patients if in dose level 1 should be withdrawn from trial treatment (please complete withdrawal form at Level 1) and treated according to local investigator choice and continue to complete CRFs.
< 30ml/min	This group of patients should be withdrawn from trial treatment (please complete withdrawal form at Level 1) and treated according to local investigator choice and continue to complete CRFs

Neurotoxicity/ototoxicity

Neurotoxicity/ototoxicity appears to be cumulative. Prior to each course, any new or progressive symptoms of peripheral neuropathy should be established.

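### Stages A2 and B: protocol sections 8.4 and 9.4.4 give different cisplatin doses for the same reduced GFR, both at Cycle 1 Day 1 and on Day 1 of later cycles

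*Protocol*

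**What the plan says.** Protocol section 8.4 contains a table headed "Laboratory values required for administration of M6620 (Berzosertib) and chemotherapy". For Stages A2 and B its estimated-GFR row has three entries:

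- Cycle 1 Day 1: "≥60mL*/min Stage A2/B". The asterisk leads to a footnote: below 60, a formal clearance is required, and 100% cisplatin may be given if the formal result is at least 50 mL/min.
- Day 1 of subsequent cycles: at least 60 mL/min, with no asterisk.
- Other M6620 days: GFR is not required.

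Section 9.4.4 has its own cisplatin table, for GFR at baseline and before Day 1. It gives 100% at 60 or more and 50% at 45–59. Cisplatin first stops in the 30–44 row: "Stop Cisplatin. This group of patients if in dose level 1 should be withdrawn from trial treatment". The text above that table says that an estimate below 60 leads to a formal test and then to the dose in the table. It adds that the formal result "takes precedent over estimated GFR for subsequent cisplatin dose calculations".

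Two other sections say where chemotherapy laboratory limits are found. Section 8.6, on cisplatin, says "Laboratory values required for administration of chemotherapy will be as per standard policy" and cites 8.4 only for M6620. Section 8.8, on laboratory values for chemotherapy, says "See table in section 8.4".

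**The concern.** There are two clashes.

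(a) **Day 1 of cycle 2 onwards.** The 8.4 table states a requirement for administration, and 8.8 applies it to chemotherapy. A patient at 45–59 mL/min does not meet it, yet 9.4.4 gives that patient half-dose cisplatin.

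(b) **Cycle 1 Day 1.** With a formal result of 50–59, the 8.4 footnote permits full dose and 9.4.4 gives half.

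Two sites could follow the protocol in good faith and give the same patient different cisplatin doses. Cisplatin is cumulatively nephrotoxic, as 9.4.4 notes, and Stage B is radical treatment, so both over-dosing and under-dosing matter to the patient. Sections 8.2 and 8.3 also state that chemotherapy dosing is the same across M6620 schedules, which calls for one dosing rule at every site.

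**Working it through.** The plan states no figure on this point, so there is nothing to reproduce. The check applies each rule to the same GFR values and then counts dose.

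**Inputs.** Cisplatin 60 mg/m² on Day 1 of each 21-day cycle: 6 cycles in A2 (section 8.2.2), and 2 induction plus 2 concurrent cycles in B (section 8.3.2). GFR rules from 8.4 and 9.4.4. Half dose = 0.5 × 60 = 30 mg/m².

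**Step 1. Later-cycle Day 1, Stages A2/B.**

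| GFR (mL/min) | 8.4 as written | 9.4.4 |
|---|---|---|
| 60 or more | requirement met | 100% = 60 mg/m² |
| 45–59 | requirement not met | 50% = 30 mg/m² |
| below 45 | requirement not met | no cisplatin |

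The rules agree outside 45–59 and disagree within it. The two cut-offs for giving no cisplatin are 60 − 45 = 15 mL/min apart.

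**Step 2. Cycle 1 Day 1, estimate below 60, formal result 50–59.** The 8.4 footnote permits 100% = 60 mg/m². Section 9.4.4 gives 50% = 30 mg/m². Below 50 the footnote is silent, so a formal result of 45–49 falls back into the Step 1 disagreement.

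**Step 3. Does any passage settle it?** Section 8.6 suggests that 8.4 is not the chemotherapy rule; 8.8 says that it is. The precedence sentence in 9.4.4 ranks formal clearance above estimated GFR. It does not rank 9.4.4 above 8.4, and it does not help when the formal result itself is 45–59.

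**Step 4. Size for one affected later cycle.** Assume that GFR is back at 60 or more by the next cycle, full dose then resumes, and there is no other reduction.

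| | Stage B (4 × 60 = 240 planned) | Stage A2 (6 × 60 = 360 planned) |
|---|---|---|
| 9.4.4 | 3 × 60 + 30 = 210 (87.5%) | 5 × 60 + 30 = 330 (91.7%) |
| 8.4, cycle delayed then given | 240 (100%) | 360 (100%) |
| 8.4, dose omitted | 3 × 60 = 180 (75%) | 5 × 60 = 300 (83.3%) |

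The 8.4 table does not say whether an unmet value means delay or omission, so both are shown. The 9.4.4 total differs from either by 30 mg/m², which is 12.5% of the Stage B plan and 8.3% of the A2 plan.

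**Step 5. Size for Cycle 1 Day 1.** The difference is 60 − 30 = 30 mg/m² in cycle 1. With full dose afterwards, the Stage B totals are 240 against 210 and the A2 totals 360 against 330.

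**The case against.** The strongest reply is that the sections can be read together: 60 is the threshold for full dose, and 9.4.4 governs below it. Much of this stands for later cycles. Section 9.4.4 is specific to cisplatin, covers each Day 1 and speaks of later dose calculations. Entry to A2 and B already needs an estimated GFR of at least 60 (section 4.1), so an absolute bar would leave the 45–59 row almost unused. The 8.4 footnote also links 60 to the full dose.

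Three things keep the point open. The table heading states a requirement for administration, and the ANC and platelet cells in the same column match section 9.4.1, where lower values mean stopping until recovery. Section 8.8 sends chemotherapy to this table. And no reading of 60 as a full-dose threshold resolves clash (b), where the footnote allows full dose at 50–59.

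A second reply is that 8.4 concerns M6620 only. Section 8.6 supports that and 8.8 contradicts it. In A2 and B, cisplatin is given on day 1 and M6620 from day 2, and GFR is not required on other M6620 days. The Day 1 GFR cell therefore bears mainly on chemotherapy.

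A reader might infer more than the documents support:

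- **A Stage B spread of 150 to 240 mg/m².** The low end, 60 + 3 × 30 = 150, needs the general sentence in 9.4, "Once the dose has been reduced, it should not be increased at a later time", to apply to GFR-based reductions after a fall before cycle 2. That is a separate question. Section 9.4.4 makes a reduction pending the formal test and then lets the formal result set the dose, which suggests recalculation.
- **An equal conflict for AST/ALT.** The later-cycle cell reads "≤2.5 X ULN or ≤5 X ULN if liver metastases", while section 9.4.3 does not interrupt capecitabine for an isolated rise below 5 × ULN. But 9.4.3 concerns capecitabine alone, and a site could hold the other drugs and continue it. At most one cell lacks a phrase.
- **Altered DLT counts or Stage B deliverability.** A hold counts as a DLT only if it lasts 7 days or more within a cycle and is due to treatment-related toxicity; the documents do not show how often that would follow. The 80% deliverability threshold would separate 75% from 87.5% only if cisplatin were scored alone, which the protocol does not specify.

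**Conclusion.** The protocol states two different cisplatin rules for reduced GFR in Stages A2 and B, and its two pointers on which applies contradict each other. For Day 1 of cycle 2 onwards the conflict band is 45–59 mL/min; for Cycle 1 Day 1 it is a formal result of 50–59. Section 9.4.4 is probably what is meant for later cycles; for Cycle 1 Day 1 the documents give no clear answer.

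The direct effect is 30 mg/m² per affected cycle, measured against a full dose (delayed in later cycles) or, in later cycles, no dose. The totals assume a single affected cycle with full dose otherwise. The documents do not say how many patients would enter either band, so no trial-level rate is given, and no effect on DLT counts, the TiTE-CRM or the primary result is claimed. It is worth correcting because it concerns the dose of a nephrotoxic drug and the correction costs little.

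**What to change.** In the next protocol amendment:

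1. Change the 8.4 GFR cell for Day 1 of subsequent cycles to: *at least 60 mL/min for full-dose cisplatin; below 60, formal clearance and dose per 9.4.3/9.4.4*.
2. Make 8.6 and 8.8 point to that one rule.
3. Set a single cisplatin dose for a formal GFR of 50–59 at Cycle 1 Day 1, so that the 8.4 footnote and the 9.4.4 table agree. Which dose is a clinical decision for the sponsor.

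Optional clarifications: say in 9.4.4 whether the no-increase sentence in 9.4 covers GFR-based reductions, and add *capecitabine alone: see 9.4.3* to the Day 1 AST/ALT cell.

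The cost is one table cell, one footnote or table row, two cross-references and, if wanted, two short clauses. No extra data, visits or analyses are needed.

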9 TOXICITY MANAGEMENT

9.1 Dose Limiting Toxicity

9.1.1 Reporting a DLT

A dose limiting toxicity is a toxicity that is considered related to M6620 (Berzosertib) or the interaction between M6620 (Berzosertib) and radiotherapy or chemoradiotherapy. **Dose limiting toxicities should be reported within 24 hours of the site becoming aware using the SAE form and scan and email as a PDF attachment to [contact] and send an email notification to [contact].** For management of M6620 (Berzosertib) toxicities see section 9.3. Chemotherapy and radiotherapy toxicities should be managed as per standard practice.

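### Protocol 8.4 and 9.4.4 give inconsistent cisplatin renal dosing in Stages A2 and B: a direct conflict at Cycle 1 Day 1 (formal clearance 50-59 mL/min) and an unclear rule at later cycles (GFR 45-59 mL/min)

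*Protocol*

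**What the plan says.** Protocol 8.4 contains a table headed "Laboratory values required for administration of M6620 (Berzosertib) and chemotherapy". In its GFR row the Cycle 1 Day 1 cell for the two chemotherapy stages asks for at least "60mL*/min Stage A2/B". The asterisk leads to a footnote: if the estimate is below 60 mL/min, a formal clearance test is required, and "100% dose cisplatin may be administered if formal result is" at least 50 mL/min. The cell for Day 1 of subsequent cycles also asks for at least 60 mL/min in Stages A2 and B, but it has no asterisk and no reduced-dose option. The third column, for other days on which M6620 is given, says that GFR is not required.

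Protocol 9.4.4 sets a cisplatin renal rule of its own. If the baseline estimate is below 60 mL/min, "a formal measure of Creatinine clearance should be performed (EDTA or 24 hour urine test) and the appropriate cisplatin dose used". The table that follows is labelled for baseline and for use before Day 1. It gives 100% at 60 mL/min or more, 50% at 45-59, cisplatin stopped at 30-44, and withdrawal from trial treatment below 30. The text adds that a formal result "takes precedent over estimated GFR for subsequent cisplatin dose calculations".

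Other sections point in different directions. Section 8.8 sends the reader to the 8.4 table for chemotherapy laboratory values. Section 8.6, on cisplatin, leaves those values to standard policy and cites 8.4 for M6620. Section 9.4.3 gives capecitabine at 100% for a GFR of 50 or more and at 75% for 30-49.

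**The concern.** Cisplatin is one of the trial's investigational products, and 9.4.4 itself describes its kidney toxicity as cumulative. A site that looks up the dose for a patient with reduced clearance should find one answer. Here, at one visit and on one test result, one section allows twice the dose that the other gives. At later cycles, where falling renal function is most foreseeable, one section can be read as forbidding the dose and the other as halving it. At stake are patient safety and consistent delivery of the chemotherapy backbone, which the protocol says stays the same across M6620 schedules.

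There is also a smaller drafting problem in the neighbouring blood-count rules. The first row of the 9.4.1 table joins its neutrophil and platelet conditions for full dose with and/or, so it overlaps the rows that stop chemotherapy.

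**Working it through.** No sample size or power figure is involved. The check sets the two sections side by side, band by band. Full-dose cisplatin is 60 mg/m² (Protocol 8.2.2 and 8.3.2), so 50% is 0.5 × 60 = 30 mg/m².

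| Visit and renal result (Stages A2/B) | Protocol 8.4 | Protocol 9.4.4 | Result |
|---|---|---|---|
| Cycle 1 Day 1, estimate at least 60 | Requirement met | 100% | Agree |
| Cycle 1 Day 1, estimate below 60, formal at least 60 | 100% permitted | 100% | Agree |
| Cycle 1 Day 1, estimate below 60, formal 50-59 | 100% permitted (60 mg/m²) | 50% (30 mg/m²) | Conflict |
| Cycle 1 Day 1, estimate below 60, formal 45-49 | 100% not permitted; no dose stated | 50% (30 mg/m²) | 8.4 silent |
| Later cycle Day 1, GFR at least 60 | Requirement met | 100% | Agree |
| Later cycle Day 1, GFR 45-59 | Below the required value; no action stated | 50% (30 mg/m²) | Unclear |

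**Cycle 1 Day 1.** The 8.4 permission starts at a formal 50, and the 9.4.4 half-dose band runs from 45 to 59. They overlap at 50-59. Ranking the formal result above the estimate does not settle the matter, because both sections already use the formal result.

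The reach is small. Entry to A2 and B requires an estimated GFR of at least 60 mL/min (Protocol 4.1). Screening takes place within 2 weeks of the first dose, with 7 more days allowed (Protocol 5.3), so 14 + 7 = 21 days at most. The conflict mainly affects a patient whose estimate drops below 60 in that interval. Because 8.4 says 100% *may* be given, a half dose satisfies both sections.

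**Later cycles.** The 8.4 heading presents its values as requirements for chemotherapy as well as M6620, and 8.8 confirms that use. A GFR of 45-59 fails the requirement, but 8.4 does not say what follows. Section 9.4.4 gives a half dose for the same band. The 8.4 row is for *estimated* GFR, so a patient with an estimate of at least 60 and a formal result of 45-59 meets 8.4 and takes 50% from 9.4.4 without difficulty. The problem is confined to estimates below 60.

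**Blood counts (9.4.1).** Take a neutrophil count of 1.2 and platelets of 60 (×10⁹/L). The neutrophil count alone satisfies the full-dose row, because its conditions are joined by and/or. The platelet count alone satisfies the next row, which stops chemotherapy. The 8.4 table lists at least 1 and at least 75 as separate requirements, so both are needed.

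**The case against.** The strongest reply is that the two sections complement each other: 8.4 gives the normal go-ahead values and 9.4 gives the adjustments. Section 9.4.3 supports this. A firm hold on all chemotherapy below 60 would leave most of its capecitabine bands unusable on Day 1. The 9.4.4 text supports it too: "In the case of a 25% deterioration in estimated renal function", a formal test is done and "pending this an appropriate dose reduction in cisplatin should be made". Section 8.6 can also be read as taking cisplatin out of the 8.4 table. This has real force for later cycles and is why that part is described as unclear rather than contradictory. It does not close the point, because the 8.4 heading and 8.8 say that the table governs chemotherapy and the cell itself mentions no reduction. For Cycle 1 Day 1 the reply fails, since the footnote itself states a dose and it differs from the 9.4.4 dose.

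A second reply is that the Cycle 1 case is rare, that a compliant action exists, and that Protocol 4.2 lets sites ask the trial office about clinical discretion. The first two parts stand and limit the size of the point. The third offers a route to an answer but does not supply one.

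A reader might infer a stronger consequence: that a site reading 8.4 as a hold would record a delay DLT where a site giving half dose on time would not, and so distort the primary endpoint. The documents do not support claiming this. The delay item in 9.1.2 needs 7 days or more *within a cycle*, and postponing Day 1 of the next cycle is arguably a delay between cycles. Section 9.1.1 also limits DLTs to toxicity "considered related to M6620 (Berzosertib) or the interaction between M6620 (Berzosertib) and radiotherapy or chemoradiotherapy". In Stage A2 a 7-day delay from cisplatin on day 22 is reached on day 22 + 7 = 29, after the 4 × 7 = 28-day window. How often the chain would complete cannot be derived.

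**Conclusion.** The inconsistency is in the current text and worth correcting. At Cycle 1 Day 1 it is a direct conflict, 60 against 30 mg/m² at a formal clearance of 50-59 mL/min, and it should be rare. At later cycles it is an ambiguity across 45-59 mL/min: half dose is the better-supported intention, and a hold is a possible reading of 8.4. The number of patients affected cannot be estimated from the documents.

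The conclusion rests on reading the 8.4 table as applying to chemotherapy, as its heading and 8.8 say. If 8.6 were meant to override that, the later-cycle ambiguity would largely disappear, but the footnote would still state a cisplatin dose that 9.4.4 does not give. The 9.4.1 wording is a separate and minor drafting error.

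**What to change.** Make 9.4.4 the single cisplatin renal rule.

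- **8.4 footnote:** replace the permission with: formal result 45-59 mL/min, 50% cisplatin per 9.4.4. If the clinical team does intend 100% at 50-59, amend the 9.4.4 band instead. One of the two must change.
- **8.4, Day 1 of subsequent cycles, Stages A2/B:** change to: at least 60 mL/min for full-dose cisplatin; below 60, cisplatin per 9.4.4 and capecitabine per 9.4.3. This removes no renal check on M6620, which in these stages is given on days other than Day 1 of a cycle, when 8.4 requires no GFR.
- **9.4.1, first row:** change and/or to *and*, so that full dose needs a neutrophil count of at least 1 and platelets of at least 75.

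The cost is one footnote, one table cell and one table row. Design, sample size and analysis are unchanged. The only decision needed is the clinical team's choice of dose at 50-59 mL/min.
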